2.4 Treatments (study treatment, rescue medication, concomitant therapies, compliance)

2.4.1 Study treatment / compliance

Study Treatment

The summaries by treatment group will be performed cumulatively by the actual treatment received (as follows) for every visit until Week 16.

Treatment groups in Treatment Period 1:

- Secukinumab 300 mg
- Secukinumab 150 mg
- Placebo

For entire treatment period, the summaries by treatment group will be performed cumulatively by the actual treatment received (as follows) for every visits till Week 52, including the patients who switched at Weeks 16, 28, 40.

Treatment groups for entire treatment period analysis:

For efficacy variables:

- Secukinumab 300 mg
- Secukinumab 150 mg 150 mg (R)
- Secukinumab 150 mg 300 mg (NR)
- Any Secukinumab 150 mg
- Placebo Secukinumab 300 mg

For safety variables

- Any Secukinumab 150 mg
- Any Secukinumab 300 mg
- Any Secukinumab

The analysis of study treatment data will be based on the Safety Set. The number of active and placebo injections will be summarized by treatment group up to Week 52.

Duration of exposure

The duration of exposure to study treatment will also be summarized by treatment group. In addition, the number and percentage of subjects with cumulative exposure levels (e.g. any exposure, ≥ 1 weeks, ≥ 2 weeks, ≥ 3 weeks, ≥ 4 weeks, ≥ 8 weeks, etc.) will be presented.

Duration of exposure of study Treatment Period 1 will be defined as the time from first dose of study treatment till the end of Treatment Period 1 (Week 16).

Duration of exposure of switched treatment group (for patients switching from placebo to secukinumab 300 mg, or secukinumab 150 mg to 300 mg) in Treatment Period 2 will be defined as the time from treatment switch to end of Treatment Period 2 (Week 52).

The duration of exposure of initial treatment group in Treatment Period 2 will be defined as the time from first dose (Week 16) till the end of Treatment Period 2 (for secukinumab 300 mg group) or until the switch (for secukinumab 150 mg group).

For patients who discontinue, this will be the patient's last visit in the corresponding treatment period.

Duration of exposure (years) = duration of exposure (days) / 365.25

Duration of exposure (100 patient years) = duration of exposure (years) / 100

The analyses of duration of exposure described above will be done for the entire study treatment periods.

2.4.2 Prior, concomitant and post therapies

Prior and concomitant therapies

Prior medications are defined as treatments taken and stopped prior to first dose of study treatment. Any medication given at least once between the days of first dose of randomized study treatment and the date of the last study visit will be a concomitant medication, including those which were started pre-baseline and continued into the period where study treatment is administered. Safety Set will be used for the analysis.

Medications will be presented in alphabetical order, by Anatomical Therapeutic Classification (ATC) codes and grouped by anatomical main group. Tables will show the overall number and percentage of patients receiving at least one treatment of a particular ATC code and at least one treatment in a particular anatomical main group.

Significant prior and concomitant surgeries and procedures will be summarized by primary system organ class and MedDRA preferred term.

Prespecified concomitant medications (Methotrexate (MTX), Folic acid, Systemic corticosteroids, Non-steroidal anti-inflammatory drugs (NSAIDs) (including selective COX-2 inhibitors), low strength opioids and acetaminophen) will be summarized by categories, route of administration and preferred term.

In addition, prior and concomitant medication data will be listed.

Rescue medication

Rescue medication is defined as medication used to control symptoms that are not adequately controlled on study treatment.

Rescue medication must not be used before completion of Week 16 assessments.

Changes in NSAIDs concomitant therapy is permitted after Week 16 assessments per investigator's clinical judgment.

Rescue medication will be summarized similarly to concomitant medication.

2.5 Analysis of the primary objective

The primary objective is to demonstrate that the efficacy of secukinumab 300 mg at Week 16 is superior to placebo in patients with active PsA based on the proportion of patients achieving an American College of Rheumatology 20 (ACR20) response.

A patient will be considered as improved according the ACR20 criteria if she/he has at least 20% improvement in the two following measures:

- Tender joint count,
- Swollen joint count.
- and at least 20% improvement in at least 3 of the following 5 measures:

- a. Patient's assessment of pain,
- b. Patient's Global Assessment of Disease Activity,
- c. Physician's Global Assessment of Disease Activity,
- d. Health Assessment Questionnaire (HAQ) score,

e. Acute phase reactant (high sensitivity C-reactive protein (hsCRP) or ESR) Primarily, CRP will be used to calculate ACR response. ESR will only be used in the event CRP is

missing.

2.5.1 Primary endpoint

The primary efficacy variable is ACR20 response (yes, no). The primary analysis time point will be at Week 16.

The primary analysis of the primary efficacy variable will be based on the Full Analysis Set.

2.5.2 Statistical hypothesis, model, and method of analysis

Let π_i denote the probability of an ACR20 response at Week 16 for treatment group j, j = 0, 1, 2, where 0 corresponds to placebo, 1 corresponds to secukinumab 150 mg, and 2 corresponds to secukinumab 300 mg. Accordingly, $\pi_i/(1 - \pi_i)$ is the odds for treatment group j, j = 0, 1, 2.

The following null hypotheses (H_{01} and H_{02}) will be tested against their corresponding alternative hypotheses (H_{A1} and H_{A2}):

 $H_{01}: [\pi_1/(1-\pi_1)]/[\pi_0/(1-\pi_0)] \le 1$ versus $H_{A1}: [\pi_1/(1-\pi_1)]/[\pi_0/(1-\pi_0)] > 1$

H₀₂: $[\pi_2/(1-\pi_2)]/[\pi_0/(1-\pi_0)] \le 1$ versus H_{A2}: $[\pi_2/(1-\pi_2)]/[\pi_0/(1-\pi_0)] > 1$

The primary efficacy variable will be analyzed at Week 16 using a logistic regression model with treatment (3 treatment groups), methotrexate usage at baseline (yes, no), and body weight (in kg) as explanatory variables (Stokes, Davis, and Koch, 2012). The odds ratios for each dose of secukinumab versus placebo, 95% confidence intervals for the odds ratios, and p-values based on the fitted model will be reported. If the p-value for a dose of secukinumab versus placebo is < 0.05 and the corresponding odds ratio is greater than 1, statistical significance in favor of that dose of secukinumab is shown.

Methotrexate usage at baseline and body weight are assumed to have possible impact on the variable, so those will be included in the logistic regression model, even though the factors will not be used to stratify at randomization.

The primary variable will also be analyzed at each time point till Week 16 using the same model.

Number and percentages of ACR20 responders will be reported for each treatment group by visit in entire treatment period up to Week 52 using oberved data. Similar summary will be provided for ACR20 using non-responder imputation.

Number and percentages of ACR20 responders will be reported for each treatment group, concomitant methotrexate usage at baseline and by visit in entire treatment period up to Week 52. Similar summary will be provided for ACR20 using non-responder imputation.

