2.2 Secondary objectives

To evaluate:

- The efficacy of secukinumab 150 mg compared to placebo at Week 16 in patients with active PsA based on the proportion of patients achieving an American College of Rheumatology 20 (ACR20) response.
- The efficacy of secukinumab 300 mg and 150 mg compared to placebo at Week 16 based on the proportion of patients with dactylitis in the subset of patients who have dactylitis at baseline.
- The efficacy of secukinumab 300 mg and 150 mg compared to placebo at Week 16 based on the proportion of patients with enthesitis in the subset of patients who have enthesitis at baseline.
- The efficacy of secukinumab 300 mg and 150 mg compared to placebo at Week 16 in subset of patients with active PsA and number of tender and swollen joints less than 10 at baseline based on the proportion of patients achieving ACR20, ACR50, and ACR70 responses
- The efficacy of secukinumab 300 mg and 150 mg compared to placebo at Week 16 based on the proportion of patients achieving ACR50 and ACR70 responses.
- The efficacy of secukinumab 300 mg and 150 mg compared to placebo at Week 16 based on the proportion of patients achieving Minimal Disease Activity (5 of the following 7 criteria: ≤ 1 tender joint, ≤ 1 swollen joint, PASI ≤ 1 or IGA mod 2011 ≤ 1 , patient assessment of pain (0-100 Visual Analog Scale (VAS)) ≤ 15 , patient global assessment of disease (VAS) ≤ 20 , HAQ-DI ≤ 0.5 , tender enthesal points ≤ 1).
- The efficacy of secukinumab 300 mg and 150 mg compared to placebo at Week 16 based on the proportion of patients achieving a PASI75, PASI90, and PASI100 responses
- The efficacy of secukinumab 300 mg and 150 mg compared to placebo at Week 16 based on the change from baseline in DAS28-CRP.
- The efficacy of secukinumab 300 mg and 150 mg compared to placebo at Week 16 based on the change from baseline in Psoriatic Arthritis Disease Activity Score (PASDAS).
- The efficacy of secukinumab 300 mg and 150 mg compared to placebo at Week 16 based on the change from baseline in SF12.
- The efficacy of secukinumab 300 mg and 150 mg compared to placebo at Week 16 based on the change from baseline in HAQ-DI.

- The overall safety and tolerability of secukinumab 300 mg and 150 mg compared with placebo as assessed by vital signs, clinical laboratory values, and adverse events (AE) monitoring.

3 Investigational plan

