9.4.2 Statistical model, hypothesis, and method of analysis

Let π_j denote the probability of an ACR20 response at Week 16 for treatment group j , $j = 0, 1, 2$, where 0 corresponds to placebo, 1 corresponds to secukinumab 150 mg, and 2 corresponds to secukinumab 300 mg. Accordingly, $\pi_j/(1 - \pi_j)$ is the odds for treatment group j , $j = 0, 1, 2$.

The following null hypotheses (H_{01} and H_{02}) will be tested against their corresponding alternative hypotheses (H_{A1} and H_{A2}):

$$H_{01}: [\pi_1/(1 - \pi_1)]/[\pi_0/(1 - \pi_0)] \leq 1 \text{ versus } H_{A1}: [\pi_1/(1 - \pi_1)]/[\pi_0/(1 - \pi_0)] > 1$$

$$H_{02}: [\pi_2/(1 - \pi_2)]/[\pi_0/(1 - \pi_0)] \leq 1 \text{ versus } H_{A2}: [\pi_2/(1 - \pi_2)]/[\pi_0/(1 - \pi_0)] > 1$$

The primary efficacy variable will be analyzed at each time point using a logistic regression model with treatment (3 treatment groups), methotrexate usage at baseline (yes, no), and body weight as explanatory variables (Stokes, Davis, and Koch, 2012). The odds ratios for each dose of secukinumab versus placebo, 95% confidence intervals for the odds ratios, and p-values based on the fitted model will be reported. If the p-value for a dose of secukinumab versus placebo is < 0.05 and the corresponding odds ratio is greater than 1, statistical significance in favor of that dose of secukinumab is shown.

The primary analysis of the primary efficacy variable will be based on the Full Analysis Set.

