9.7 Sample size calculation

The sample size was calculated based on the primary efficacy variable (i.e., ACR20 response) for the primary comparison (i.e., secukinumab 300 mg versus placebo). ACR20 response rates of 50% for secukinumab 300 mg and 20% for placebo (corresponding to an odds ratio of 4) at Week 16 were assumed, based on results from AIN457F2312 (FUTURE 2) study. Using a continuity-corrected chi-squared test, an allocation ratio of 2:1, a two-sided significance level of 0.05, and a power of 0.90, approximately 88 patients in secukinumab 300 mg group and 44 patients in placebo group will be needed (nQuery Advisor 7.0). Assuming a loss to follow-up rate of 10% and a 2:2:1 allocation ratio (secukinumab 300 mg: secukinumab 150 mg: placebo), the total number of randomized patients will be approximately 250 (100 on secukinumab 300 mg, 100 on secukinumab 150 mg, and 50 on placebo)

10 Ethical considerations

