1.2 Study objectives and endpoints

Table 1.2-1: Objectives and endpoints

Objective	Endpoint
Primary objective	
To demonstrate that the efficacy of secukinumab 300 mg at Week 16 is superior to placebo in adult patients with active PsA based on the proportion of patients achieving an American College of Rheumatology 20 (ACR20) response.	ACR20 response (yes, no)
Secondary objectives	

To evaluate the efficacy of secukinumab 150 mg compared to placebo at Week 16 in patients with active PsA based on the proportion of patients achieving an American College of Rheumatology 20 (ACR20) response.	ACR20 response (yes, no)
To evaluate the efficacy of secukinumab	Dactylitis (yes no)
300 mg and 150 mg compared to placebo at	
Week 16 based on the proportion of patients	
withdactylitis in the subset of nations who	
have dactylitis at baseline.	
To evaluate the efficacy of secukinumab	Enthesitis (yes, no)
300 mg and 150 mg compared to	
placebo at Week 16 based on the proportion	
of patients with enthesitis in the subset of	
patients who have enthesitis at baseline.	
To evaluate the efficacy of secukinumab	ACR20, ACR50, and ACR70 responses
300 mg and 150 mg compared to	
placebo at Week 16 in subset of patients	
with active PsA and number of tender and	
swollen joints less than 10 at baseline based	
on the proportion of patients achieving	
ACR20, ACR50, and ACR70 responses.	
To evaluate the efficacy of secukinumab	ACR50 and ACR70 responses
300 mg and 150 mg compared to placebo at	
Week 16 based on the proportion of patients	
achieving ACR50 and ACR70 responses.	
To evaluate the efficacy of secukinumab	Minimal Disease Activity (yes, no) (5 of the
300 mg and 150 mg compared to placebo at	following 7 criteria: ≤ 1 tender joint, ≤ 1
Week 16 based on the proportion of patients	swollen joint, PASI ≤ 1 or IGA mod 2011 ≤ 1 ,
achieving Minimal Disease Activity (5 of	patient assessment of pain (0-100 Visual
the following 7 criteria:	Analog Scale (VAS)) ≤ 15 , patient global
≤ 1 tender joint, ≤ 1 swollen joint, PASI ≤ 1 or	assessment of disease (VAS) ≤20, HAQ-DI
IGA mod 2011 ≤ 1 ,, patient assessment of	≤ 0.5 , tender entheseal points ≤ 1)
pain (0-100 Visual Analog Scale (VAS))	
\leq 15, patient global assessment of disease	
$(VAS) \leq 20$, HAQ-DI ≤ 0.5 , tender entheseal	
points ≤1)	
To evaluate the efficacy of secukinumab	PASI75, PASI90, PASI100 responses (yes,
300 mg and 150 mg compared to	no)
placebo at Week 16 based on the proportion	
of patients achieving a PASI75, PASI90,	

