2.1 Data analysis general information

Data will be analyzed by Novartis Product Life-Cycle Services and/or a designated Contract Research Organization.

It is planned that the data from all centers that participate in this protocol will be combined, so that an adequate number of patients will be available for analysis. Analysis datasets and statistical outputs will be produced using the most recent SAS[®] Version 9.4 (SAS Institute Inc., Cary, NC, USA), and stored in Novartis global programming & statistical environment (GPS).

As the primary analysis time point is Week 16, there will be a database lock after all patients have completed the Week 16 visit and data are clean and complete. At that time, only the statistician and programmer(s) from Novartis and/or a designated CRO will be unblinded in order to perform the analysis. Results from the analyses of all data through Week 16 will be shared internally. For publication purposes, summary results from the Week 16 primary analysis time point may be shared with the health care community; however, individual subject-level data will remain blinded until the end of the trial. A final database lock will occur when all patients have completed the study.

Summary statistics for continuous variables will include mean, standard deviation, standard error of mean, median, 25th and 75th percentiles, interquartile range, minimum, and maximum at each time point. Summary statistics for discrete variables will be presented in the number and percent of patients in each category. Summary statistics will also be presented graphically wherever applicable. If not otherwise specified, p-values and confidence interval (CI) will be presented as two-sided and the default level of significance will be set to 0.05 (two-sided). For all continuous variables (efficacy and safety), change from baseline and percentage change from baseline by visit will also be presented.

Data analyses will be presented by treatment group. Efficacy and safety data for the placebocontrolled period (or the entire Treatment Period as appropriate) will be presented by the following 3 treatment groups. Patients may be included in more than one treatment group for some analyses (e.g. exposure-adjusted adverse events over the entire treatment period).

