2.6 Analysis of the key secondary objective

There is no key secondary objective.

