2.7.2 Statistical hypothesis, model, and method of analysis

Dactylitis and enthesitis

Analyses of dactylitis and enthesitis will be performed at each time point up to Week 16. The data for the subgroup of patients who have dactylitis at baseline (similarly for enthesitis) will be used and the data will be analyzed using a logistic regression model with treatment (3 treatment groups), methotrexate usage at baseline (yes, no), and body weight as explanatory variables. The odds ratios for each dose of secukinumab versus placebo, 95% confidence interval for the odds ratios, and p-values based on the fitted model will be reported.

Number and percentages of patients with presence of enthesitis will be reported for each treatment group and by visit in entire treatment period up to Week 52. Similar summary will be provided for patients with presence of enthesitis using non-responder imputation.

The above analyses will be done on Dactylitis Subset,

ACR20, ACR50, and ACR70 responses

ACR20, ACR50, ACR70 responses at each time point up to Week 16, and in subsets of patients with active PsA and number of tender and swollen joints < 10 and ≥ 10 at baseline will be analyzed using a logistic regression model with treatment (3 treatment groups), methotrexate usage at baseline (yes, no), and body weight as explanatory variables. The odds ratios for each dose of secukinumab versus placebo, 95% confidence intervals for the odds ratios, and p-values based on the fitted model will be reported.

Additionally, ACR50 and ACR70 responses will be analyzed as analogous to primary efficacy variable at each time point up to Week 16.

Number and percentages of ACR50 and ACR70 responders will be reported for each treatment group, concomitant methotrexate usage at baseline and by visit in entire treatment period up to Week 52. Similar summary will be provided for ACR50 and ACR70 using non-responder imputation.

Number and percentages of ACR50 and ACR70 responders in subsets of patients with active PsA and number of tender and swollen joints < 10 and \geq 10 at baseline will be reported for each treatment group and by visit in entire treatment period up to Week 52. Similar summary will be provided for ACR50 and ACR70 using non-responder imputation.

Minimal Disease Activity

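### The ACR20 significance rule also covers the secondary 150 mg comparison, with no order or label, and SAP Section 4 reports no changes although at least one is visible

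*SAP*

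**What the plan says.** **The rule.** Protocol 9.4.2 and SAP 2.5.2 set out two null hypotheses for ACR20 at Week 16, one for 150 mg and one for 300 mg. They then give a single rule: "If the p-value for a dose of secukinumab versus placebo is < 0.05 and the corresponding odds ratio is greater than 1", then "statistical significance in favor of that dose of secukinumab is shown". Neither section orders the doses, makes one test depend on the other, or splits alpha.

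**The status of each dose.** The primary objective (Protocol 2.1, SAP 2.5) names 300 mg only. Protocol 9.7 sizes the trial "for the primary comparison (i.e., secukinumab 300 mg versus placebo"). The 150 mg ACR20 comparison is listed under Protocol 2.2 ("The efficacy of secukinumab 150 mg compared to placebo at Week 16 in patients with active PsA") and as a secondary objective in SAP 1.2 ("To evaluate the efficacy of secukinumab 150 mg compared to placebo at Week 16 in patients with active PsA"). SAP 2.6 adds: "There is no key secondary objective".

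**The other secondary variables.** Each gets a p-value per dose, and under SAP 2.1 "the default level of significance will be set to 0.05 (two-sided"). No hierarchy is given and the p-values are not called nominal. SAP 2.7.2 says that "ACR50 and ACR70 responses will be analyzed as analogous to primary efficacy variable", without stating whether the declaration rule goes with the analysis. The only statement about not adjusting alpha (Protocol 3.5 and 9.6, SAP 2.14) concerns the Week 16 analysis time point and the two database locks, not the two doses.

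**Changes from the protocol.** SAP Section 1 promises that departures from the protocol are documented. Section 4, which is reserved for them, reports none.

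**The concern.** The rule sits in the primary-analysis section and uses confirmatory language, but it reaches a comparison that the same documents class as secondary. A study report that follows it literally could state that significance has been shown for 150 mg even if 300 mg had failed. The reader could not tell a controlled claim from an uncontrolled one. The same ambiguity touches ACR50 and ACR70 through the reference back to the primary variable.

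An empty Section 4 has a related cost. A reader who relies on it would not learn that a protocol analysis was narrowed, that another may have been dropped, or which Week 16 tests were added late.

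**Working it through.** **1. The plan's own sample size.** Inputs from Protocol 9.7: 50% v 20%, allocation 2:1, two-sided 0.05, power 0.90, continuity correction. With k = 2, pooled rate 0.4 and difference 0.3:

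- Uncorrected placebo n = [1.96·√(1.5·0.4·0.6) + 1.2816·√(0.2·0.8 + 0.5·0.5/2)]² / 0.3² = 38.4.
- Corrected n = (38.4/4)·[1 + √(1 + 2·3/(38.4·2·0.3))]² = 43.3, so 44 on placebo and 88 on 300 mg, as stated.
- After 10% loss: 44/0.9 → 49 and 88/0.9 → 98. The total 98 + 98 + 49 = 245 is consistent with about 250.

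The sample size therefore rests on the 300 mg comparison alone and is not in question.

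**2. Neither dose works, asymptotically.** At 100/100/50 the two statistics share the placebo arm, so their correlation is √[(100/150)·(100/150)] = 0.667. Two-sided 0.05 with an odds ratio above 1 puts 2.5% in the favourable tail of each test. P(at least one) = 1 − Φ₂(1.96, 1.96; 0.667) = 0.0425, against 0.025 for 300 mg alone.

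**3. Neither dose works, exactly.** Test: unadjusted Wald test of the log odds ratio, without the model's covariates. Let q3 and q1 be the chances, given x0 placebo responders, that 300 mg and 150 mg are declared. P(any) = Σ p(x0)·[1 − (1 − q3)(1 − q1)]. The common response rates are assumptions.

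| Common rate | Any declaration | 300 mg | 150 mg only |
|---|---|---|---|
| 20% | 3.30% | 1.93% | 1.37% |
| 25% | 3.56% | 2.10% | 1.46% |
| 30% | 3.74% | 2.21% | 1.54% |
| 35% | 3.90% | 2.30% | 1.61% |

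The excess over 300 mg alone is the last column, 1.4 to 1.6 percentage points.

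**4. 300 mg works as planned, 150 mg does not (50% v 20% v 20%).** By the same exact test, 150 mg is falsely declared in 1.9% of trials. It is falsely declared after a failed 300 mg test in about 0.00001%. A gate would remove only the second figure.

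**5. Both doses work (both assumed 50% v 20%).** Power is 96.0% for each dose. 150 mg is declared after a failed 300 mg test in 2.7% of trials. Requiring 300 mg to succeed first takes 150 mg power from 96.0% to 96.0 − 2.7 = 93.3%. Power for 300 mg does not change.

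**6. Section 4 against the text.**

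- *Cochran-Mantel-Haenszel (CMH) test.* Protocol 9.4.4 compares each dose with placebo. SAP 2.5.4 compares 300 mg only, but its rule still awards significance to whichever dose passes.
- *Ordinal analysis.* Protocol 9.5.1 plans a proportional-odds model for dactylitis and enthesitis in all patients. SAP 2.7.2 has only the logistic model in patients affected at baseline, 2.7.4 plans no supportive analyses, and 5.4.3 has no ordinal model. Section 2.13 and the SAP front pages are not in the text available to me.
- *Very Low Disease Activity (VLDA).* SAP 2.7.2 plans tests against placebo up to Week 16. The protocol's list of variables does not include it. The damaged revision history appears to date its definition to November 2018, after the Week 16 lock.

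**The case against.** The strongest reply is that there is one primary objective, one powered comparison and one primary time point, so the trial's confirmatory claim is already protected. That stands. A reader might infer that the primary type I error is inflated. It is not: the 300 mg test is unaffected, and a failed 300 mg test remains a failed primary objective.

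It is also fair to say that the excess needs both doses to be ineffective. Protocol 3.3 makes that unlikely for 150 mg, with earlier Week 24 ACR20 rates of 50.0% v 17.3% and 51.0% v 15.3%. Nor should the 2.7% in step 5 be read as false positives. There 150 mg truly works, so these are correct rejections outside the planned primary claim.

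A third reply is that the 150 mg hypothesis and its rule are in the protocol, so removing the declaration withdraws a prespecified inference. That is a real cost and the reason for the milder option under the fix. It does not justify leaving the status of a 150 mg declaration unstated.

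Two further inferences go beyond the text. The revision history might suggest that the Week 16 tests of HAQ-DI ≤ 0.5 and of the minimal clinically important difference (MCID) are post hoc. What it records for them is a Week 52 analysis, so it does not show that the Week 16 tests in SAP 2.11 were new. And the ordinal analysis cannot be called dropped with certainty while Section 2.13 is unseen.

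**Conclusion.** The point holds at low severity. The rule permits a declaration for a secondary comparison with no error control across doses and no label. Its size is 4.2% against 2.5% asymptotically, or 3.3-3.9% against 1.9-2.3% exactly. This applies only if neither dose works, under the assumed common rates and an unadjusted test at 100/100/50. If 300 mg performs as planned, the lack of a gate adds essentially nothing. This is mainly a question of labelling.

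The Section 4 point does not depend on unseen text: the CMH narrowing alone contradicts an entry of no changes. The missing ordinal analysis and the late dating of the VLDA tests are supported by the visible text, but remain subject to what cannot be seen.

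**What to change.** 1. In SAP 2.5.2 and 2.5.4, limit the significance declaration to 300 mg versus placebo at Week 16. Report 150 mg ACR20 and the other secondary p-values as nominal and not adjusted for multiplicity, with estimates and intervals.
2. At the least, make no 150 mg declaration unless 300 mg succeeds.
3. Record whichever is chosen in SAP Section 4 as a departure from Protocol 9.4.2 made after the Week 16 lock. Either change can only remove a claim.
4. In Section 4, list the CMH narrowing and reconcile Protocol 9.4.4 with SAP 2.5.4. List the ordinal dactylitis and enthesitis analysis as dropped, unless it appears in the unseen text.
5. Label the Week 16 VLDA tests as apparently added after the lock, again subject to the unseen text. No such label is warranted for the HAQ-DI ≤ 0.5 and MCID tests.

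The cost is wording in the SAP and study report, with no loss of alpha, sample size or 300 mg power. The downside is no formal 150 mg claim under item 1. Under item 2 the claim is weaker: 150 mg power falls from 96.0% to 93.3% if both doses reach 50% v 20%.
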